9.2 Per protocol population

The Per Protocol (PP) population will include all subjects who received at least one dose of IMP and excludes subjects with <80% treatment compliance or who have other major protocol deviations impacting the study endpoints. Deviations for exclusion from the PP population due to inadequate exposure to IMP or completeness of primary efficacy endpoint will be determined during blinded review meeting. Per-protocol population will be defined for each study period separately.

The PP population is the primary population to analyse efficacy endpoints. Demographic and baseline characteristics of the PP population will also be presented.

9.3 Safety population

The safety population consists of all randomised subjects who received at least one dose of IMP and had at least one post dose safety assessment. The safety population will be used for the analysis of safety and tolerability. Subjects will be analysed as treated, regardless of the randomised treatment assigned, if this differs from that to which the subject was randomised.

9.4

10 Analysis Variables

10.1 Population Flags

Population flags will be finalized and authorized by the Study Statistician and Sponsor during the blind review meeting prior to database lock as per definitions provided in Section 9. These flags will be included in the analysis datasets.

10.2 Treatment

The following treatment variables along with corresponding numeric equivalents will be included as core variables in all analysis datasets:

- Planned / Actual Treatment Sequence : LAT8881 60 mg-Placebo, Placebo-LAT8881 60 mg •

Planned / Actual Treatment: LAT8881 60 mg, Placebo

10.3 Visits

Analysis visits will be defined as follows within each study period:

Visit as per Protocol	Study Period	Analysis Visit
Visit 1 (Days -28 to -1)	Pre-Treatment	Screening

Day 1, Visit 2	Period 1	Visit 2/Visit 5
Day 14, Visit 3	Period 1	Visit 3/Visit 6
Day 28, Visit 4	Period 1	Visit 4/Visit 7
Day 50, Visit 5	Period 2	Visit 2/Visit 5
Day 63, Visit 6	Period 2	Visit 3/Visit 6
Day 77, Visit 7	Period 2	Visit 4/Visit 7
Day 91, Visit 8 or Early Termination	-	EOS / Early Termination

For NPRS scores, post-baseline summaries will be based on weeks within study:

- Week 1 (Days 1-7 and 50-56)
- Week 2 (Days 8-14 and 57-62)
- Week 3 (Days 15-21 and 63-69)
- Week 4 (Days 22-28 and 70-76)

Timepoints will be included for NPRS data as ‘Pre-dose’ and ‘X hours post-dose’ for subjects with measurements taken at timepoints. NPRS will be derived using diary scores as detailed in Section 10.15.

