4.5 Treatment allocation

The IMP is supplied as opaque, size 0 capsules, in a high-density polyethylene bottle containing 60 capsules. One bottle will contain sufficient capsules for one treatment period. Each capsule contains 30 mg LAT8881 plus [REDACTED] excipients. Placebo capsules contain the excipients [REDACTED] only (without LAT8881).

On Day 1, after the first baseline period, eligible subjects will be enrolled and randomised to LAT8881 or placebo. They will receive the investigational medicinal product (IMP) twice daily for four weeks (Days 1 to 28). On the morning of Day 28 they will return to the clinic for their end of first treatment visit and will take an IMP capsule in the morning during their clinic visit. They will take their final IMP dose for this treatment period in the evening.

The first treatment period will be followed by a washout period of two weeks (Days 29 to 42 inclusive) and then a second baseline period of one week (Days 43 to 49 inclusive). Over these days (i.e. Days 29-49 inclusive) subjects will not take any IMP.

On Day 50, subjects will return to the clinic and cross over to receive the second treatment (either LAT8881 or placebo, whichever treatment was not received in the first treatment period) twice daily for four weeks (Days 50 to 77). On the morning of Day 77, they will return to the clinic for their end of

second treatment visit and will take an IMP capsule in the morning during their clinic visit. They will take their final IMP dose for this treatment period in the evening.

5 Assessment Schedule

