7.1 Primary Efficacy Endpoints

1. *Absolute change in mean pain score, using an 11 point NPRS, from baseline to the last week of each treatment period. Pain is recorded once daily in a subject diary in the evening, and should reflect the subject's average pain over the last 24 hours*

Baseline mean pain for each subject is defined as the mean of the last five available ratings of daily pain, recorded in each baseline period.

End of treatment mean pain for each subject is defined as the mean of the last five available ratings of daily pain, recorded in the last 7 days of each 4 week treatment period.

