10.15 Efficacy Endpoints

10.15.1 NPRS Mean Scores

NPRS mean daily score ranging from 0 (no pain) to 10 (worst imaginable pain) will be derived at baseline and weeks 1 to 4 for each treatment period. Baseline mean score is defined in Section 10.12.2. The mean daily pain score each week during treatment is the arithmetic mean of the last 5 available ratings of daily pain recorded in each 7 day period within each treatment period. Standard deviations (SD) of the mean scores will be included in analyses datasets. If a subject has <5 non-missing ratings, the mean score will be set to missing for the respective week.

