11.6.1.2 Mixed Effect Regression Model

A mixed effects regression model using a covariance pattern will be fitted to the absolute change from baseline mean NPRS scores at weeks 1, 2, 3 and 4 within each treatment period for the PP population. This analysis will provide the results for the primary efficacy endpoint (change from baseline to week 4) and for the secondary endpoint (change from baseline to weeks 1, 2 and 3).

The model will have fixed effects for period, week, treatment and the interaction between week and treatment. Baseline mean pain score within each period by treatment combination will be included as a covariate. A random effect for subject will be included to capture the repeated measures nature of the design.

Least squares means and corresponding 95% confidence intervals (CI) will be presented for the mean change from baseline for LAT8881, Placebo and difference between LAT8881 vs. placebo at each visit.

P-values for testing the null hypothesis that the difference in least squares means between LAT8881 and placebo at each visit is 0 will be declared statistically significant if the p-value < 0.05.

The covariance pattern will take into account the covariance between observations in different treatment periods and the covariance between observations within the same period (i.e between weeks).

```
proc mixed data=;  
class <subject> <study period> <treatment> <week>; model  
<change> = <baseline> <study period> <week> <treatment>;  
random <subject> <subject>*<period>; lsmeans <treatment>  
<week> / pdiff;  
run;
```

The model will also be fitted to the absolute change from baseline in mean NPRS ratings for the FAS population. Extent of sensitivity analyses of missing data patterns to be undertaken will be decided during the blinded review meeting. In DDP: Tables 14.2.2.1 to 14.2.2.2

11.6.1.2.1 *NPRS at timepoints*

A mixed effects regression model using a covariance pattern will be fitted to the absolute change from pre-dose NPRS scores at timepoints 0.5, 1, 2, 4 and 6 hours post-dose at baseline and week 4 visits within each study period for the per-protocol subjects with NPRS collected at timepoints in baseline and week 4 visits.

The model will have fixed effects for period, week, timepoint and the interaction between week and timepoint. Pre-dose pain score within each week will be included as a covariate. A random effect for subject will be included to capture the repeated measures nature of the design.

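### SAP 10.3 spreads the Period 2 NPRS weeks over 27 days instead of 28, so Period 2 Week 4 is not the primary endpoint window

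*SAP*

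**What the plan says.** - **Length of the period.** SAP 4.5 describes the second treatment as "four weeks (Days 50 to 77"), which is 28 days inclusive. SAP 10.14 also computes the assigned dose on 28 days.
- **Primary endpoint.** SAP 7.1, like protocol 9.1, averages the last five available daily ratings "recorded in the last 7 days of each 4 week treatment period".
- **Weekly means.** SAP 10.15.1 averages the last five ratings "recorded in each 7 day period within each treatment period". It adds: "If a subject has <5 non-missing ratings, the mean score will be set to missing for the respective week".
- **Model.** SAP 11.6.1.2 fits Weeks 1 to 4 together and states: "This analysis will provide the results for the primary efficacy endpoint (change from baseline to week 4").
- **Day ranges.** SAP 10.3 gives Week 1 as Days 1-7 and 50-56, then "Week 2 (Days 8-14 and 57-62"), "Week 3 (Days 15-21 and 63-69") and "Week 4 (Days 22-28 and 70-76"). It refers to Section 10.15 for the derivation of the scores.
- **Visit pairing.** The analysis visit table in SAP 10.3 pairs Day 1 with Day 50, Day 14 with Day 63, and Day 28 with Day 77.

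**The concern.** The Period 1 ranges divide 28 days into four full weeks; the Period 2 ranges do not. The endpoint rules in SAP 7.1, 7.2 (item 3) and 10.15.1 are correct, but none of them gives day numbers. SAP 10.3 is the only place where numbered days are assigned to weeks, so it is what a programmer would code.

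Two things are at stake. First, Week 4 supplies the primary result and the comparison is within subject across periods, so the two periods should use the same window. As printed, Period 2 uses a window that is not the stated endpoint. Second, the five-rating minimum is harder to meet in a six-day week, so Week 2, a secondary timepoint, would lose more values in Period 2 than in Period 1.

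**Working it through.** **1. Day counts (end - start + 1).**

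| | Period 1 | Period 2 as printed | Period 1 + 49 |
|---|---|---|---|
| Week 1 | 1-7 (7) | 50-56 (7) | 50-56 (7) |
| Week 2 | 8-14 (7) | 57-62 (6) | 57-63 (7) |
| Week 3 | 15-21 (7) | 63-69 (7) | 64-70 (7) |
| Week 4 | 22-28 (7) | 70-76 (7) | 71-77 (7) |
| Total | 28 | 27 | 28 |

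The stated length reproduces: 77 - 50 + 1 = 28. The offset of 49 comes from the SAP's own visit table: 50 - 1 = 63 - 14 = 77 - 28 = 49. As printed, Day 14 lies in Week 2 but its pair, Day 63, lies in Week 3. Day 28 lies in Week 4 but its pair, Day 77, lies in no week.

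**2. Effect on the Week 4 mean.** The printed window (70-76) and the endpoint window (71-77) share six of seven days. With a complete diary, the last five ratings are Days 72-76 as printed and Days 73-77 under the endpoint definition. Four of the five coincide, so

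mean(73-77) - mean(72-76) = (Day 77 score - Day 72 score) / 5.

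A 1-point difference between those two days moves the subject's value by 1/5 = 0.2 points. If Day 77 is not rated and the rest is complete, both windows average Days 72-76 and nothing changes.

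**3. Effect on missing weeks.** The documents give no diary completion rate. Assume each day is completed independently with probability q:

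- at least 5 of 7: 21q⁵(1-q)² + 7q⁶(1-q) + q⁷
- at least 5 of 6: 6q⁵(1-q) + q⁶

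| q (assumed) | 5 of 7 | 5 of 6 | Week 2 missing, Period 1 | Week 2 missing, Period 2 as printed |
|---|---|---|---|---|
| 95% | 99.6% | 96.7% | 0.4% | 3.3% |
| 90% | 97.4% | 88.6% | 2.6% | 11.4% |
| 80% | 85.2% | 65.5% | 14.8% | 34.5% |

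Week 2 valid in both periods, printed against corrected:

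- q = 90%: 0.974 × 0.886 = 0.863 against 0.974² = 0.949. Of 44 completers, about 38 against 42.
- q = 80%: 0.852 × 0.655 = 0.558 against 0.852² = 0.726. Of 44 completers, about 25 against 32.

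Week 4 has seven days under either window, so its validity is the same (97.4% or 85.2%) if Day 77 is rated as often as other days. If Day 77 is never collected, Days 71-77 hold only six usable days and validity is 88.6% or 65.5%.

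**4. Visit windows.** Visit 7 is Day 77 ± 1. With complete diaries limited to treatment days, compare each fixed window with the subject's true last five treatment-day ratings:

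| Last treatment day | Ratings replaced, 70-76 | Ratings replaced, 71-77 |
|---|---|---|
| 76 | 0 | 0 |
| 77 | 1 | 0 |
| 78 | 2 | 1 |

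The visit window does not cancel the error. The corrected range is never worse and is better in two of the three cases.

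**The case against.** **The governing rules are right.** SAP 7.1 with 4.5 implies Days 71-77, SAP 7.2 item 3 and 10.15.1 imply seven-day weeks, and 10.3 introduces its list for summaries. This is one faulty list against several concordant rules. That is fair, and it is why the correction is not in doubt. But the model uses the same Weeks 1 to 4, and no other section gives day numbers. The SAP therefore contradicts itself on the primary window.

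**Day 77 may have been left out on purpose.** Visit 7 takes place that morning. The protocol synopsis mentions a morning diary entry, the last diary check described is at that visit (protocol 8.6.3), and Visit 8 (protocol 8.7.1) lists none. The Day 28 evening rating, by contrast, sits in a diary that continues to Day 50. The asymmetry is real, and it stands as a reason to check that the rating exists. It does not justify the printed list: no such intention is stated, protocol 2.2 schedules evening ratings throughout treatment, and leaving out Day 77 would still contradict SAP 7.1.

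**The effect is small and the larger figures are hypothetical.** This stands for the primary endpoint. The Week 2 losses depend on assumed completion rates and shrink at 95%. The mixed model also keeps values from a single period, so the both-period counts describe lost precision and not lost subjects.

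**Fixed Days 71-77 match the endpoint only nominally.** This is true when treatment ends on Day 78, as step 4 of the working shows, but the printed range is worse in that case.

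**Conclusion.** The concern holds. The Period 2 ranges in SAP 10.3 total 27 days, leave out Day 77, give Week 2 six days and start Weeks 3 and 4 a day early. The Week 4 range conflicts with the primary endpoint in SAP 7.1 and protocol 9.1. These facts need only a day count and rest on no assumption.

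The consequence for the primary estimate is probably small: one of five averaged ratings, in one period. Both treatments occur in Period 2 and the model has a period effect, so no systematic treatment bias is expected. The Week 2 loss is one of precision at a secondary timepoint, and its size depends on independent daily completion at rates the documents do not give. It should be fixed because it concerns the derivation of the primary endpoint and costs almost nothing to correct.

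**What to change.** Before database lock, change the Period 2 ranges in SAP 10.3 to Days 57-63 (Week 2), 64-70 (Week 3) and 71-77 (Week 4). Week 1 (50-56) stays. Week 4 then agrees with SAP 7.1 and protocol 9.1, and both periods use the same weeks.

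Alongside this, confirm that the scheduled Day 77 evening rating is recorded and retrieved after Visit 7, because the corrected Week 4 relies on it. If it turns out not to be available, the SAP should say so openly, since Week 4 would then rest on at most six ratings in Period 2.

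The cost is three day ranges in the SAP, the matching lines of the derivation program and one check of diary collection. The sample size does not change.

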10.4 Study Periods

Duration between initial screening and end of first treatment (Days -28 to 28) is considered as study period 1; washout (Days 29 to 42) is considered as washout period; duration between second baseline period up to end of study visit (Days 43 to 91) is considered as study period 2. Study periods will be considered to set analysis visits.

10.5 Completion Flags

- Subjects are considered to have completed period 1 when Day 28 visit is completed.
- Subjects are considered to have completed period 2 when Day 77 visit is completed.
- Subjects are considered to have completed study when EOS at Day 91 visit is completed.

10.6 Prior and Concomitant Medications

Medications that ended before first dose of IMP (LAT8881 or placebo) in the first treatment period are considered as prior medications. If medications are ongoing or they start on or after first dose of IMP (LAT8881 or placebo) they are considered concomitant.

Medications that started on or after first dose of IMP in treatment period 1 or during wash-out will be counted in the first treatment period and allocated to the treatment received in treatment period 1.

Medications that started on or after first dose of IMP in treatment period 2 will be counted in the second treatment period and assigned to the treatment received in treatment period 2. If medication occurred in first study period and continued to second, it will be counted in both study periods (as 'New' in period 1 and 'Ongoing' in period 2).

Programming note for concomitant medications:

- Period 1, Ongoing - if CM start date is prior to first dose of IMP in period 1 and end date is on or after first dose of IMP in period 1.
- Period 1, New - if CM start date is on or after first dose of IMP and before first IMP date in period 2.
- Period 2, Ongoing - medications that were new or ongoing in period 1, with end date on or after first IMP date in period 2.
- Period 2, New - if CM start date is on or after first dose of IMP in period 2.

Concomitant medications will either be flagged as "Ongoing" or "New" within a study period, but not in both.

10.7 Rescue Medications

Rescue medications will be flagged for analysis. Additionally, cumulative dose in milligrams (mg) will be calculated within each study period. If a subject has ongoing rescue medication in both study periods, then the cumulative dose within each study period will be calculated.

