13.5.3 Analgesic use

Paracetamol (rescue medication) use at baseline and weekly over the treatment period will be listed for each subject. The average weekly and cumulative dose of rescue paracetamol medication in each treatment period will be summarised by visit and treatment.

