7.2 Secondary Efficacy Endpoints

1. *Change in NPRS score at 0.5, 1, 2, 4 and 6 hours after the first dose of IMP in each treatment period, compared with the score recorded no more than 60 minutes before the first dose of IMP in that treatment period (PK subjects only)*
2. *Change in NPRS score at 0.5, 1, 2, 4 and 6 hours after a single dose of IMP, following four weeks treatment with IMP in each treatment period, compared with the score recorded no more than 60 minutes before this dose (PK subjects only)*
3. *Change in mean pain scores from baseline after 1, 2 and 3 weeks of dosing with IMP in each treatment period, using an 11 point NPRS. Pain scores at weeks 1, 2 and 3 are defined as the mean of the last five available ratings of daily pain in the subject diary, recorded in the previous 7 days of treatment*
4. *30% responder rate, based on the proportion of subjects achieving $\geq 30\%$ reduction in mean NPRS from baseline to the end of 4 weeks treatment in each treatment period*
5. *50% responder rate, based on the proportion of subjects achieving $\geq 50\%$ reduction in mean NPRS from baseline to the end of 4 weeks treatment in each treatment period*
6. *Maximum change in mean NPRS from baseline after 1, 2, 3 or 4 weeks treatment in each treatment period*
7. *Change in functioning from baseline to the end of 4 weeks treatment in each treatment period, as measured by the BPI interference scale*
8. *Change in pain characteristics and intensity from baseline to the end of 4 weeks treatment in each treatment period, as assessed by the SF-MPQ-2*
9. *Change in neuropathic pain symptoms from baseline to the end of 4 weeks treatment in each treatment period, as assessed by NPSI*

10. *Change in emotional functioning from baseline to the end of 4 weeks treatment in each treatment period, as assessed by the BDI-II*
11. *PGIC at the end of each four week treatment period*
12. *Paracetamol (rescue medication) use per week over each treatment period compared with the preceding baseline*

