11.5.1 Rescue Medications

Number and percentage of subjects who have taken any rescue medication will be summarized along with cumulative dose (mg) taken by treatment overall and within each study period. Extent of further analyses of rescue medications will be decided during the blinded review meeting.

Rescue medication will be listed by subject. In

DDP: Table 14.1.5.3, Listing 16.2.4.6

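### As SAP 10.4 defines 'study period', the rescue paracetamol totals include off-treatment days, and the SAP does not specify the weekly, baseline-referenced endpoint

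*SAP*

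**What the plan says.** The endpoint is item 12 of SAP 7.2 (also Protocol 9.2): paracetamol "use per week over each treatment period compared with the preceding baseline". Protocol 13.5.3 plans listings of use at baseline and by week, and adds: "The average weekly and cumulative dose of rescue paracetamol medication in each treatment period will be summarised by visit and treatment".

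The SAP's own derivation is different. SAP 10.7 says that "cumulative dose in milligrams (mg) will be calculated within each study period". SAP 11.5.1 reports the number and percentage of users, "summarized along with cumulative dose (mg) taken by treatment overall and within each study period", and leaves the extent of any further rescue analysis to the blinded review meeting.

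SAP 10.4 supplies the day ranges. For the first period it says: "Duration between initial screening and end of first treatment (Days -28 to 28) is considered as study period 1". For the second it says: "duration between second baseline period up to end of study visit (Days 43 to 91) is considered as study period 2". The fortnight between them, Days 29 to 42, is washout and belongs to neither. The section closes with a purpose: "Study periods will be considered to set analysis visits". SAP section 12, which lists changes from the protocol's analyses, does not mention rescue medication.

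**The concern.** Two things go wrong if a programmer follows these sections literally.

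First, the total mixes on-treatment and off-treatment days. The two baseline weeks, which the endpoint uses as comparator, are added into the quantity that should be compared with them. The 14 days after the last dose are added to Period 2. The two windows differ in length, and the Period 1 window varies between subjects with the length of screening.

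Second, the rescue section contains no weekly rate, no rescue baseline and no change from baseline. The general rules do not fill the gap. SAP 10.13 calculates change from baseline for all efficacy endpoints, but it needs a baseline. SAP 10.12.2 defines the baseline for secondary endpoints as the most recent measurement before dosing, which does not suit a quantity accumulated over a week.

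Rescue use answers secondary objective 10 in SAP 3.2. It also bears on how the pain result is read: the protocol permits up to 4 g of paracetamol a day, and the primary model in SAP 11.6.1.2 has no term for it.

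**Working it through.** **Inputs.** Study periods and washout: SAP 10.4. Treatment days 1-28 and 50-77: Protocol 5.1. Screening plus first baseline of up to 4 weeks and a maximum participation of 17 weeks: Protocol 5.6. Days are nominal, with no Day 0.

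**Check of the day counts against the protocol's own figure.**
- Study period 1: 28 (Days -28 to -1) + 28 (Days 1 to 28) = 56 days.
- Washout: 14 days.
- Study period 2: 7 (Days 43 to 49) + 28 (Days 50 to 77) + 14 (Days 78 to 91) = 49 days.
- Sum: 56 + 14 + 49 = 119 days = 17 weeks, as Protocol 5.6 states.

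**On-treatment share = treatment days / days counted.** The shortest screening is not stated. I assume 8 days (Day -8 to Day -1), because Stage 1 ends on Day -8.

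| Window | Full 28-day screening | Assumed 8-day screening |
|---|---|---|
| Period 1 | 28/56 = 50.0% | 28/36 = 77.8% |
| Period 2 | 28/49 = 57.1% | 28/49 = 57.1% |
| Both | 56/105 = 53.3% | 56/85 = 65.9% |

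**Dilution of a relative effect.** Assume one unit per day off treatment and on placebo, and 0.7 units per day on active (a true 30% reduction). With full screening:
- Period 1: 1 - (28 + 19.6)/56 = 15.0%.
- Period 2: 1 - (21 + 19.6)/49 = 17.1%.
- Both: 1 - (47.6 + 40.6)/105 = 16.0%.

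With the assumed 8-day screening, Period 1 shows 8.4/36 = 23.3% and both periods together 16.8/85 = 19.8%. The absolute difference is 28 × 0.3 = 8.4 units in each period, whatever off-treatment days are added.

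**Window length.** Constant use of 1 g a day with no treatment effect totals 56 g in Period 1 (36 g with 8-day screening) and 49 g in Period 2. At full screening Period 2 is lower by 7/56 = 12.5% for no reason but the calendar.

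**Other uses of the term in the SAP.**
- The 10.3 table places the screening visit under a pre-treatment label and assigns the end-of-study visit to no period.
- 10.14 derives compliance within each study period but sets the assigned dose at 28 days × 60 mg.
- 10.16.1 speaks of the end of four weeks' treatment in each study period.
- 10.6, immediately before the rescue section, starts each period at first dose and counts washout medications in period 1. Carried over to rescue dose, that gives roughly Days 1-49 and 50-91, with shares 28/49 = 57.1%, 28/42 = 66.7% and 56/91 = 61.5% overall.

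So 10.4 and the rule in 10.6 both bring in off-drug days. Only the usage in 10.14 and 10.16.1 points to the 28 treatment days.

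**The case against.** The best defence is that 10.4 exists to set analysis visits, by its own last sentence, and that the SAP often writes 'study period' where it means treatment period. A sensible programmer might total Days 1-28 and 50-77 without being told. That stands as a reason for caution about intent. It does not remove the problem: 10.4 is the only place where the term is given day ranges, and the weekly rate and baseline comparison are missing from the rescue section even on the narrow reading.

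Three stronger readings are tempting, and the documents do not support them.
- A reader might infer that the endpoint will never be computed. SAP 11.5.1 leaves further rescue analyses open, 10.13 has a general change rule, and Protocol 13.5.3 still plans the average weekly dose. The Data Display Plan, which lays out the table, is not available. What can be said is that the SAP does not specify the endpoint.
- A reader might infer that only about half the counted days are on treatment. For Period 1 that needs the full 28-day screening window. It also presumes that rescue use is quantified during Days -28 to -8, which no section shows.
- A reader might infer that the treatment comparison is biased. With constant off-treatment use the absolute difference is intact, and with balanced sequences the unequal windows create a period difference and no treatment difference. The relative effect is still diluted. Variable screening length adds noise, and sequences that become unbalanced, for example by dropout before Period 2, would let window length into the overall treatment totals.

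**Conclusion.** The point holds in this form: the rescue totals, built on the SAP's only dated definition of a study period, measure something other than the stated secondary endpoint, and the SAP's rescue section does not specify that endpoint on any reading. Section 12 does not declare the departure from Protocol 13.5.3.

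Under 10.4 the on-treatment share is 50% to 78% in Period 1, 57% in Period 2 and 53% to 66% overall. The lower ends assume full 28-day screening and the upper ends an assumed 8 days. The fall from a true 30% reduction to an apparent 15% to 17% assumes full screening and constant use off treatment; it concerns the relative effect only. These figures depend on 10.4 being the governing definition, which the SAP's inconsistent usage leaves uncertain. The missing weekly rate and baseline do not depend on it. The sponsor should correct this, but it does not touch the primary endpoint's definition or model.

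**What to change.** Before unblinding, amend the SAP as follows.
1. In 10.7 and 11.5.1, replace 'study period' with the treatment windows Days 1-28 and Days 50-77.
2. Report rescue dose as mg per week: total mg divided by days observed, times 7. With complete data this is the 28-day total divided by 4.
3. Define the rescue baseline as mg per week over Days -7 to -1 for the first period and Days 43-49 for the second.
4. Tabulate weekly use and change from the preceding baseline, by treatment.
5. Reconcile 'study period' across 10.3, 10.4, 10.6, 10.14 and 10.16.1.

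A mixed model like that used for the other secondary endpoints is optional, since the protocol plans only listings and summaries for rescue use.

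The cost is SAP wording and one table, provided rescue doses are recorded with dates. Protocol 13.5.3 presumes this, but the diary is described for pain ratings only and the assessment schedules have no row for rescue dose, so the sponsor should confirm the data source.
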